4.2 Study Drug Administration

Study drug will consist of identical tablets containing either clopidogrel 75 mg or placebo. The supply of study drug will be provided to the patient following treatment group assignment. Patients will be instructed to take the first dose of study drug by mouth - clopidogrel 300 mg (4 pills) or placebo (4 pills), within 1 calendar day following fistula creation surgery. After that, the patient will take clopidogrel 75 mg (1 pill) or placebo (1 pill) daily. Study drug will be continued until 6 weeks after fistula creation surgery.

4.3 Initiation of Fistula Use

There are no data on the optimal time of fistula maturation and therefore decisions about when to initiate use of the new fistula will be left to the patient's nephrologist and/or vascular surgeon.

4.4 Intercurrent Events and Interruptions in Treatment

At the time of enrollment, patients will be provided with an information card containing a description of the study and study personnel contact information. The information card should facilitate rapid communication with study personnel if adverse events occur or treatment interruptions need to be considered.

4.4.1 Bleeding

Bleeding will be classified as minor, intermediate, major, life-threatening or fatal. Minor bleeding events are episodes of bleeding that do not require an event-related visit or follow-up or discontinuation of the study drug. Intermediate bleeding is a bleeding event that does not meet criteria for a major bleed but requires an event-related visit with a health care provider or temporary discontinuation of study medication. Examples of minor or intermediate bleeds might include superficial cuts, abrasions, bruises, epistaxis, or vaginal bleeding events. The presence of a hemocult positive stool alone that leads to non-emergent evaluation such as a colonoscopy and is not associated with a ≥ 2 g/dl drop in hemoglobin or the need for a transfusion will be considered an intermediate bleeding event. Major bleeding is defined as a confirmed retroperitoneal, intra-articular, intraocular, or intracranial bleed or any bleed that leads to a drop in hemoglobin by 2 g/dl and requires hospitalization or the need for a transfusion. Life-threatening bleeding is any bleed that leads to a drop in hemoglobin of ≥ 5 g/dl, requires emergency surgical intervention, causes a symptomatic intracranial hemorrhage, or requires a transfusion of more than 4 units of packed RBCs or whole blood. Fatal bleeding is any bleed that causes or precipitates death.

Management of bleeding should be handled as for a patient on aspirin. For minor episodes of bleeding (e.g., superficial abrasion or nose bleed), conservative measure to control the bleeding should suffice without the requirement for discontinuing study medication. Short-term discontinuation of study medication during an intermediate bleeding episode with re-institution when stable is allowed. If the patient has a major or life-threatening bleed the study medication will be discontinued and not restarted. In the event of a cerebrovascular accident occurring during active treatment, computed tomography or magnetic resonance imaging should be performed to exclude intracerebral hemorrhage. For intermediate bleeds the decision to stop study drug will be made by the physician(s) caring for the patient. If the patient has a major or life-threatening bleed the study medication will be discontinued and not restarted unless the bleed is caused by either a surgical procedure or trauma and it is established 1) that the cause of bleeding has been eradicated, and 2) that the bleeding event does not reflect an underlying bleeding tendency or predispose to recurrent bleeding. Study drug resumption in this situation must be approved by the physician(s) caring for the patient. Bleeding events will be actively monitored and recorded by the study coordinator throughout the patient's participation on the study. An expert panel will review all major and life-threatening bleeds as well as a randomly selected subset of other bleeding events.

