3.4 Blinding

Treatment assignment will be masked to both patients and study personnel. Matching clopidogrel and placebo will be provided by Bristol-Myers Squibb and Sanofi-Synthelabo. One potential source of unblinding is prolonged hemostasis time after removal of dialysis needles at the termination of dialysis. Although it is possible that clopidogrel may prolong bleeding time and result in difficulty achieving hemostasis after removing dialysis needles, this should be an issue in only the subset of patients already receiving hemodialysis prior to enrollment in the study. Based on the demonstration that clopidogrel did not prolong the time to hemostasis in a group of nine hemodialysis patients⁴⁵, we do not expect inadvertent unblinding due to such events.

We anticipate that unblinding may be required in the following two circumstances: 1) prior to the performance of emergency surgery, and 2) if there is life-threatening hemorrhage where the transfusion of platelets to reverse the antiplatelet effects of therapy is indicated. When it is absolutely necessary that a study medication code be released, the Data Coordinating Center will reveal the medication for a given patient to the study nephrologist at the facility. After unblinding, the patient should be continued in the trial on study medication if possible. Given the short duration of study drug administration, we anticipate that the number of patients requiring unblinding will be small.

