4.4.2 Surgery or Other Invasive Procedures

If the patient requires elective surgery or other invasive procedures with a bleeding risk, study medication should be stopped 7 days prior to the procedure and resumed the day after the procedure if there has not been inordinate bleeding and if the physician performing the procedure agrees. Because of the short duration of study drug administration, elective procedures should be delayed until completion of study drug if such a delay is felt to be safe and not burdensome to the patient. If the patient requires emergent surgery where there is risk for bleeding (e.g., neurosurgery, hip replacement, abdominal surgery), study medication should be discontinued and consideration should be given to revealing the medication code and administering platelet transfusion if the patient has been receiving active drug.

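### Section 4.4.1 gives the rule on restarting study drug after a major or life-threatening bleed both with and without an exception, and section 3.4 does not fit with 4.4.1 or 4.4.2

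*Protocol*

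**What the plan says.** Four sections of the protocol bear on study drug after a serious bleed or an unblinding.

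- **Section 4.4.1, first statement:** "If the patient has a major or life-threatening bleed the study medication will be discontinued and not restarted". No exception is given.
- **Section 4.4.1, second statement, three sentences later in the same paragraph:** after the same opening, the medication "will be discontinued and not restarted unless the bleed is caused by either a surgical procedure or trauma and it is established" that two conditions hold. The cause of the bleed must have been removed, and the event must not point to a bleeding tendency or make a further bleed likely. It adds: "Study drug resumption in this situation must be approved by the physician(s) caring for the patient".
- **Section 4.4.4, item 3:** major bleeding is listed among the events that end study drug without ending study participation. The surgery or trauma exception is not mentioned.
- **Section 3.4:** unblinding is expected in two circumstances, "prior to the performance of emergency surgery" and "if there is life-threatening hemorrhage where the transfusion of platelets to reverse the antiplatelet effects of therapy is indicated". It then says: "After unblinding, the patient should be continued in the trial on study medication if possible".
- **Section 4.4.2:** for emergent surgery with a risk of bleeding, "study medication should be discontinued and consideration should be given to revealing the medication code". It says nothing about resuming afterwards. For elective procedures it does give resumption conditions.

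**The concern.** Section 5.5 names bleeding as the main expected risk of clopidogrel, so re-exposure after a serious bleed is a rule that centres will look up and apply. The protocol gives them more than one answer.

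The disputed case is foreseeable. Every randomized patient has just had fistula surgery, and study drug starts within one calendar day of it. A bleed caused by a surgical procedure is exactly where the two statements in 4.4.1 part ways.

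Three things are at stake. The first is patient safety, because patients with the same event may be re-exposed at one centre and not at another. The second is exposure, and with it the comparison of bleeding between arms. The third is the secondary analysis in section 8.2.2.2, which is limited to patients not deliberately taken off study drug during the six weeks. Who belongs to that set depends on how these rules are applied.

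**Working it through.** No figure in the plan is involved, so the check sets the instructions side by side for each kind of event.

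| Event | 4.4.1, first statement | 4.4.1, second statement | Other sections | Result |
|---|---|---|---|---|
| A. Major or life-threatening bleed, not from surgery or trauma, no unblinding | Stop, no restart | Stop, no restart | 4.4.4 item 3: cessation for major bleeding | Consistent |
| B. Bleed from surgery or trauma, but a condition fails or approval is withheld, no unblinding | Stop, no restart | Stop, no restart | As A | Consistent |
| C. Bleed from surgery or trauma, both conditions met and approval given, no unblinding | Stop, no restart | Stop, restart allowed | 4.4.4 item 3: cessation, no exception mentioned | Contradictory on restart |
| D. Life-threatening hemorrhage with unblinding, outside the exception | Stop, no restart | Stop, no restart | 3.4: continue if possible | 3.4 conflicts with both statements |
| E. Life-threatening hemorrhage with unblinding, within the exception | Stop, no restart | Stop, restart allowed | 3.4: continue if possible | 3.4 can be squared with the second statement only |
| F. Emergent surgery with bleeding risk and unblinding, no serious bleed | Not applicable | Not applicable | 4.4.2: stop, silent on resumption; 3.4: continue if possible | Not aligned; resumption left open |

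Four observations follow.

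1. The contradiction inside 4.4.1 is confined to rows C and E, and it concerns restart. Both statements require the drug to be stopped when the bleed occurs.
2. Of the two unblinding circumstances in 3.4, life-threatening hemorrhage produces a real conflict with 4.4.1 (row D). Emergency surgery produces an ambiguity with 4.4.2 (row F).
3. The rows can overlap. Section 4.4.1 counts a bleed that needs emergency surgery as life-threatening, so one patient can fall under 3.4, 4.4.1 and 4.4.2 at once.
4. For the secondary analysis, a patient in row D leaves the set if 4.4.1 is followed and could stay in it if 3.4 is followed without a stop. In row C both statements stop the drug, so membership turns on whether a stop followed by a restart counts as deliberate discontinuation. Section 8.2.2.2 does not say; a separate analysis plan may.

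Section 11.6 applies sections 4.4.1 to 4.4.4 to the pilot study, so the duplicated rule reaches that study too. The pilot is open-label, so the unblinding conflict does not arise there.

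**The case against.** The strongest reply is that this is a leftover duplicate sentence. The second statement repeats the first and adds its exception, so a reasonable reader takes it as the full rule. The exception is permissive, so a centre that never restarts complies with both statements. In 3.4 the words *if possible* allow stopping, and the sentence may mean only that unblinding alone is no reason to leave the trial or the drug. Safeguards exist: restart needs the treating physician's approval, an expert panel reviews all major and life-threatening bleeds, and the External Advisory Committee considers adverse events by arm.

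Much of this limits the point, and several stronger readings that a reader might infer are not supported:

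- **That 4.4.2 contradicts 4.4.1.** It does not. Its instruction for emergent surgery points the same way; the mismatch is with 3.4.
- **That every major bleed from surgery or trauma falls under opposite instructions.** Only those meeting both conditions, with approval, do so.
- **That centres could do opposite things under 4.4.1 while the patient is bleeding.** Both of its statements stop the drug; the difference comes later, at restart.
- **That 3.4 requires continuation.** It makes continuation the default and permits stopping.
- **That continuing drug after unblinding biases the examination-based primary outcome.** Allocation becomes known through the unblinding, whether or not the drug continues. Section 3.4 releases the code to the study nephrologist at the facility and expects few such cases, and the primary analysis keeps patients in their randomized groups.

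What the reply does not remove is that the text never says which statement in 4.4.1 governs, that 4.4.4 omits the exception, and that 3.4 defaults to continuing where 4.4.1 defaults to stopping. The expert panel's review and the committee's comparisons are not stated to decide a restart in the individual patient.

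**Conclusion.** The point holds as an internal inconsistency in operative safety rules. There is one contradiction on restart within 4.4.1, for bleeds that meet the exception. There is one conflict between 3.4 and 4.4.1, for life-threatening hemorrhage that leads to unblinding. There is one misalignment between 3.4 and 4.4.2, for emergent surgery. Section 4.4.4 item 3 adds an omission.

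The number of patients affected cannot be estimated, because the protocol gives no expected counts of major bleeds, emergency operations or unblindings. The effect on the primary analysis is likely small, given intent-to-treat analysis and the protocol's own expectation that unblinding will be rare. The case for correction rests mainly on patient safety and consistent conduct across centres, and secondarily on exposure and the secondary analysis set. It assumes that centres read each section as binding as written, since no order of precedence among the sections is stated.

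**What to change.** Sections 3.4, 4.4.1, 4.4.2 and 4.4.4 must be reconciled. Which clinical rule applies is for the trial's clinical leadership to decide.

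- State the chosen rule on stopping and restarting once, in 4.4.1, and delete the duplicate sentence.
- Have 3.4, 4.4.2 and 4.4.4 item 3 refer to that statement instead of giving their own version, and have 4.4.2 say what applies to resumption after emergent surgery.
- In 3.4, separate remaining in follow-up from remaining on study medication. Sections 2.2 and 4.4.4 already make that distinction, so only the wording of 3.4 needs to be brought into line.
- Say whether a stop followed by a permitted restart counts as deliberate discontinuation in the secondary analysis of section 8.2.2.2.

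The cost is a short amendment, the review-board approval that section 10.1 requires before a change takes effect, and a memo to the centres. Sample size, visits and the primary analysis are unchanged.

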4.4.2 Surgery or Other Invasive Procedures

If the patient requires elective surgery or other invasive procedures with a bleeding risk, study medication should be stopped 7 days prior to the procedure and resumed the day after the procedure if there has not been inordinate bleeding and if the physician performing the procedure agrees. Because of the short duration of study drug administration, elective procedures should be delayed until completion of study drug if such a delay is felt to be safe and not burdensome to the patient. If the patient requires emergent surgery where there is risk for bleeding (e.g., neurosurgery, hip replacement, abdominal surgery), study medication should be discontinued and consideration should be given to revealing the medication code and administering platelet transfusion if the patient has been receiving active drug.

4.4.3 Concomitant Medications

Patients should not receive any other antiplatelet or antithrombotic agents other than intra-dialytic heparin during the 6 weeks following fistula creation. Specifically, aspirin, non-steroidal anti-inflammatory drugs, dipyridamole, sulfipyrazone, and warfarin are not to be used. Oral or intravenous glucocorticoids at a dose greater than the equivalent of prednisone 15 mg per day should not be used. Acetaminophen, codeine, or other analgesics not containing aspirin or NSAIDs may be used for pain. If the proscribed agents are required (e.g., warfarin for deep venous thrombosis or atrial fibrillation, aspirin for new cardiovascular event) during the period of study drug administration, study medication should be discontinued and the patient should continue to be followed. For patients on aspirin prior to enrollment, the aspirin should be discontinued seven days prior to fistula creation surgery and resumed after the 6 week study drug administration period.

4.4.4 Discontinuation of Therapy

Events leading to cessation of study drug, but not termination from the study will include:

1. Removal from hemodialysis because of transplantation, recovery of renal function, or use of other dialysis modality.
2. A medical event which contraindicates continued use of an antiplatelet agent during the six week study drug period.
3. Any bleeding episode which contraindicates the continued use of antiplatelet agents during the six week study drug period. Such events include, but are not limited to, major bleeding defined as confirmed retroperitoneal, intra-articular, or cerebral hemorrhage or any bleeding

episode resulting in a 2 g/dl decrease in the hemoglobin concentration and requiring hospitalization or transfusion.

4. An adverse event attributed to the study medication without other etiology that does not respond to medical management.
5. An acute cardiovascular event requiring antiplatelet therapy.
6. Native fistula thrombosis during the six-week study drug administration period. Thrombosis must be confirmed by a member of the study team or by the patient's vascular surgeon. Participation in the study will end 30 days after discontinuation of the study drug if fistula patency is not restored by thrombectomy or thrombolysis. If fistula patency is restored, the patient will remain off study drug, but will remain in the study until the fistula suitability for dialysis is ascertained.

4.4.5 Events Leading to Withdrawal from the Study

A patient will be withdrawn from the study for the following reasons:

1. The patient leaves the participating dialysis unit and cannot be followed in another dialysis unit.
2. The patient is judged lost to follow-up after repeated attempts to contact have failed.
3. Withdrawal of consent.
3. Death.

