2.2 Design

The trial is a randomized, double-blind, placebo-controlled multi-center trial with a parallel treatment design. Patients with chronic renal failure who are on chronic hemodialysis or anticipated to begin chronic hemodialysis within 6 months will be randomized within one calendar day following creation of a new upper extremity native AV fistula to receive either clopidogrel or placebo for six weeks. Randomization will be on a 1:1 active drug:placebo allocation, and will be stratified by Clinical Center and location of AV fistula (forearm vs upper arm). Both patients and study personnel will be masked to treatment assignment. The sample size is 1284 patients, to be recruited at seven Clinical Centers over a 4-year period. Study drug administration will begin within one calendar day following native AV fistula creation and continue for 6 weeks following surgery. The primary outcome measure is fistula patency at the end of the 6-week study drug administration period. A secondary outcome measure is fistula suitability for dialysis.

A follow-up evaluation will be conducted six weeks following creation of the AV fistula. Fistula patency (primary outcome) will be ascertained at that visit. Contact will be made with the patient and/or dialysis unit on a monthly basis thereafter to obtain data related to the fistula suitability for dialysis outcome. All randomized patients who undergo creation of a native fistula will be followed regardless of whether or not they remain on their assigned treatments. Participation in the study will end once the fistula suitability outcome has been ascertained. Fistula suitability outcome ascertainment will occur during the fourth month following fistula creation for those patients who are either on chronic hemodialysis at the time of fistula creation or begin hemodialysis within 4 months of fistula creation. If dialysis is not initiated within 4 months of fistula creation, ascertainment of fistula suitability for dialysis will occur during the first month

of hemodialysis. If the fistula has not been used at the time of the suitability assessment, but may be used in the future, the patients will continue to be followed until it is determined whether the fistula is actually used.

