6. PRIMARY OUTCOME MEASURE

The primary outcome will be unassisted patency six weeks after fistula creation. Fistula patency will be determined by physical examination of the fistula performed by trained study personnel. The fistula will be classified as patent if a bruit is present throughout systole and diastole. The bruit must be detectable along the vein at least 8 centimeters proximal to the arteriovenous anastomosis. In a quality control subset of patients the outcome will be independently assessed by at least one trained member of the study team and a second person.

The fistula patency outcome will be ascertained at 6 weeks in all patients except those in whom study drug was discontinued because of fistula thrombosis prior to six weeks. To allow patients with fistula thrombosis and no restoration of patency to complete study participation within 30 days of study drug discontinuation, the fistula patency outcome assessment may be completed at any time within the 30 days following study drug discontinuation.

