11.8 Events Leading to Withdrawal from the Pilot Study

A patient will be withdrawn from the pilot study for the following reasons:

1. Follow-up during the study period is not possible because the patient moves to a distant location.
2. The patient is judged lost to follow-up after repeated attempts to contact have failed.
3. Withdrawal of consent.
4. Death.

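### The dialysis-unit withdrawal rule in section 4.4.5 makes no exception for the six-week patency examination, so some patients who could still be examined would be withdrawn

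*Protocol*

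**What the plan says.** The list in section 4.4.5 is mandatory: "A patient will be withdrawn from the study for the following reasons". Item 1 reads "The patient leaves the participating dialysis unit and cannot be followed in another dialysis unit". Item 2 separately covers patients who are lost after repeated failed contact; the remaining items are withdrawn consent and death. None of the items carries a time limit.

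On follow-up in general, section 2.2 states: "All randomized patients who undergo creation of a native fistula will be followed regardless of whether or not they remain on their assigned treatments".

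On the primary outcome, section 6 states: "Fistula patency will be determined by physical examination of the fistula performed by trained study personnel". It then fixes who is assessed: "The fistula patency outcome will be ascertained at 6 weeks in all patients except those in whom study drug was discontinued because of fistula thrombosis". No other exception is named there. Section 4.1 places this examination at the second study visit.

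Section 4.4.4 lists events that stop study drug without ending study participation. Its first item is "Removal from hemodialysis because of transplantation, recovery of renal function, or use of other dialysis modality".

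The pilot used a different rule for relocation (section 11.8): "Follow-up during the study period is not possible because the patient moves to a distant location".

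**The concern.** Item 1 judges whether a patient can be followed solely by whether a dialysis unit can follow the patient. That suits the suitability outcome in section 7.1, which depends on machine blood flow over 12 dialysis sessions. It does not suit the first six weeks, when the outcome that matters is an examination by study staff.

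Take a patient who changes unit at week 3. Suppose the new unit cannot take part in follow-up, but the patient still lives within reach of the study clinic. Both conditions of item 1 are met, so the patient is to be withdrawn, and the six-week examination is not done although it could have been.

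Two kinds of data are at stake. The first is the primary outcome in an intent-to-treat comparison. The second is bleeding, which section 5.5 names as the major expected risk of clopidogrel. Section 4.4.1 ties bleeding monitoring to the patient's participation, so it ends on withdrawal. A constraint that serves a secondary outcome would thus end collection of the primary outcome and of the main safety data.

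**Working it through.** **1. What each part of the follow-up needs**

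| Data | Where defined | Dialysis unit needed? |
|---|---|---|
| Patency at six weeks (primary) | 4.1, 6 | No: bruit heard by study personnel at a study visit |
| Bleeding and other adverse events to six weeks | 4.4.1, 5.3 | No: study coordinator, and review at the six-week visit |
| Suitability for dialysis (secondary) | 5.4, 7.1 | Yes: blood flow recorded during dialysis sessions |
| Monthly contacts with patients, physicians and units | 5.4 | Partly, and these start only after the six-week visit |

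Nothing due up to week 6 depends on a dialysis unit.

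**2. Whom item 1 adds before week 6**

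Item 2 already withdraws patients who cannot be contacted. Before week 6, item 1 therefore adds only patients who can be contacted but have no unit that can follow them. They fall into two groups: those too far away to attend, for whom a missing examination is unavoidable, and those who could attend, for whom it is caused by the rule alone.

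**3. Consistency with other sections**

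- Section 6 requires patency in all patients with one exception, study drug stopped for thrombosis. Item 1 creates a second exception that section 6 does not name. This is the firmest conflict.
- Section 2.2 says all randomized patients with a fistula are followed. Its qualifying clause concerns treatment rather than units, but the main statement is universal.
- Section 4.4.4 item 1 keeps in the study a patient who leaves hemodialysis altogether, for instance after a transplant. Such a patient has no hemodialysis unit at all, yet stays. A patient who only changes unit can be removed.

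**4. The sample size, reproduced first**

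Inputs from section 8.1: 25% thrombosis on placebo, a 30% reduction (to 17.5%), power 85%, two-sided 0.05, drop-in 3%, drop-out 3%, loss 5%, inflation 2.7%.

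- Diluted placebo rate: 0.25 × 0.97 + 0.175 × 0.03 = 0.24775.
- Diluted clopidogrel rate: 0.175 × 0.97 + 0.25 × 0.03 = 0.17725.
- The two-proportion formula with pooled variance under the null and no continuity correction gives 604 per arm.
- 604 × 1.027 / 0.95 = 653 per arm, about 1306 in total. That is 1.7% above the stated 1284, which is close enough to count as reproduced. Unpooled variance gives 1297.

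**5. What extra loss would cost**

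The protocol gives no rate of withdrawal under item 1, so the total loss below is an assumed range. Effective size per arm is 642 × (1 − loss) / 1.027.

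| Total loss | Power at N = 1284 |
|---|---|
| 0% | 86.2% |
| 5% (planned) | 84.5% |
| 8% | 83.3% |
| 10% | 82.5% |
| 15% | 80.3% |

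From 5% to 10% loss, power falls by 2.0 points over 5 points of loss, or 0.4 per point. If withdrawals under item 1 stay inside the planned 5% (0.05 × 1284 = 64 patients), the planned power is unaffected.

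**The case against.** The strongest reply is that the rule is narrower than it looks. Changing unit alone triggers nothing; the patient must also be impossible to follow in any other dialysis unit, and that unit need not be a participating one. Inclusion criterion 6 admits only patients expected to stay at a participating facility for at least six months. Sections 4.1 and 5.4 draw later data from patients, physicians and other sources as well as units, so a unit that withholds records does not by itself make a patient impossible to follow. Some who meet both conditions will also be out of reach for an examination. A 5% loss is already planned. All of this stands, and it is why the effect is probably small. It does not supply the missing exception.

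The pilot comparison also has limits. The pilot had no suitability outcome and did not require an expected stay at a facility, so its different rule is not a contradiction. It shows only that the sponsor already has wording based on whether follow-up is possible.

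On lost data, national databases can still supply hospitalization and death (sections 4.5 and 5.4), subject to any consent needed under section 10.2. They do not supply patency or the protocol's bleeding classes. The intent-to-treat statement in section 8.2.2.2 concerns the group in which patients are analyzed and does not promise complete outcomes, so it is not itself breached.

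**Conclusion.** The point holds as a defect in a stated rule: item 1 lacks an exception for the six-week examination and, followed literally, discards primary and bleeding data that could be obtained. It is minor. The number affected is not given and is probably small.

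A reader might infer more than the protocol supports:

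- That leaving a participating unit is enough for withdrawal. Item 1 has a second condition.
- That only patients already on dialysis at enrollment are exposed. Section 5.3 item 5 provides for dialysis starting before the six-week visit, so a patient not yet on dialysis at enrollment can acquire a unit and then leave it.
- That a definite share of the 5% allowance is used up, or that most such losses are avoidable. No transfer rate is given, so neither can be stated.
- That the sample size or power is wrong. The 1284 reproduces, and its power stands while total loss stays within 5%.
- That the loss biases the comparison. Treatment is masked, and the protocol gives no reason for unit transfers to differ by arm.

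The conclusion assumes that sites apply section 4.4.5 as written. A site that gave priority to section 6 would examine the patient anyway, and the two sections would then be applied differently across sites.

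**What to change.** Restrict item 1 of section 4.4.5 to suitability follow-up after the six-week visit. Add a sentence that, before that visit, leaving a dialysis unit does not end participation. The six-week examination and the adverse-event contacts then go ahead unless the patient withdraws consent, dies, cannot be contacted, or cannot attend because of a distant move. For that last case, the criterion in section 11.8 can be adapted. This brings section 4.4.5 into line with sections 2.2, 4.4.4 and 6. It concerns participation and data collection only and changes nothing about study drug.

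The cost is a short amendment with IRB approval at each center (section 10.1), plus the effort of bringing a few transferred patients to a visit already in the schedule. No new visit, measurement or change in sample size is needed.
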